8.1. Withdrawal Procedures

If the decision to withdraw a subject occurs at a study visit, regular clinic visit procedures will be conducted as well as the additional termination procedures as described in section 8.2. If it is determined via a phone call that withdrawal is appropriate or if the subject is dropping out, we will ask the subject to attend an exit visit to return study product and equipment (e.g. cell phone if

issued), complete questionnaires, product accountability and safety assessments and to receive their final study payment.

If the subject refuses an exit visit, we will request that at the minimum, study investigational products be returned and product accountability be completed. We will also stress the importance of being able to assess safety measures for the subject's safety.

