8.2. Early Termination

If a participant decides to withdraw from the study prior to completion or if they are withdrawn by the PI or LMM due to safety concerns, they will be scheduled for an early termination visit. If the participant is seen within the window of a regularly scheduled visit, all measures for that visit will be collected. Additional questionnaires and safety measures may be obtained (urine sample for biomarkers and pregnancy screen, CES-D, and BDI-II if appropriate) if not scheduled during the normal visit. If the subject is seen outside of a regularly scheduled visit window, the following measures will be obtained:

Physiological measures collected and recorded on paper, and entered into REDCap at the end of the visit:

- 1. BrAC
- 2. Weight
- 3. CO
- 4. Blood Pressure
- 5. Heart Rate
- 6. Pregnancy test (if applicable)

Biological specimens collected, stored, and entered into CENIC Biosample Collection Platform:

- 1. Spot urine sample for assessing baseline anatabine:
 - Participants will be asked to provide a urine sample in the lab for biomarker assessment. Samples will be stored at temperatures approximately at -20°C (UPenn) or -80°C (Wake Forest). Urine samples will be sent regularly to be analyzed and stored at the University of Minnesota.
- 4. First void urine sample for smoking biomarker assessment. Participants will be asked to bring a sample (first void urine of the day) for biomarker assessment. Samples will be stored at temperatures approximately at -20°C (UPenn) or -80°C (Wake Forest). Urine samples will be send quarterly to be analyzed and stored at the University of Minnesota. Total nicotine equivalents and mercapturic acids will be assessed. If a participant forgets to bring his/her urine sample, then the spot urine sample will be used.

Assessments administered via interview and entered into REDCap by the interviewer:

- 1. Concomitant Medications
- 2. Adverse Event Form, if applicable
- 3. Health Changes Questionnaire
- 4. IVR Review of Daily Call and follow-up on missing and unusual reports and Timeline Follow-back Questionnaire; if needed
- 5. Intention to Quit Smoking and Vaping
- 6. Drug Use Questionnaire, 1 month version

Assessments administered on paper and kept as a source document only:

- 1. BDI, if applicable
- 2. GAD 2 week monitoring, if needed

Assessments administered directly via REDCap:

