The following additional assessments will be completed by all early termination participants, if not part of the usual measures scheduled for the regularly scheduled visit:

- 1. CESD
- 2. Alcohol Use Questionnaire, 1 month version
- 3. Environmental and Social Influences on Tobacco Use Questionnaire
- 4. End of Study Questionnaire

The data collected during the termination visit will be used as appropriate given the days outside of visit window, subject use of study product, measures of safety or other considerations to be determined in data analysis.

9. Assessment Descriptions

- 1. Tobacco Use History and Nicotine Exposure, derived from the Population Assessment of Tobacco and Health (PATH) allowing comparisons with a nationally representative sample of smokers measures variables such as smoking rate (current and maximum), cigarette brand, age of initiation of smoking, number of quit attempts, duration of quit attempts and duration of smoking and history of use of other tobacco and nicotine products.
- 2. *Demographics* asks about age and gender, race, ethnicity, current occupation and usual occupation, and income.
- Brief Medical History Questionnaire to assess medical history and current health diagnoses, symptoms and past health problems including psychiatric and substance abuse and medication use.
- 4. *Medical History Follow-up Questionnaire* will be completed by study staff to further assess current diagnoses, symptoms or past health problems.
- 5. *Concomitant Medications* lists medications (prescription, over-the-counter and supplements) and doses that are taken 30 days prior and during the study.

6. PrimeMD - Patient Health Questionnaire (PHQ), a brief multi-choice questionnaire developed as a screening and diagnostic tool for mental health disorders of depression, anxiety, alcohol, for primary care physicians (somatoform and eating disorder questions are not used in this study).

- 7. Centers for Epidemiological Studies-Depression 20-item scale (CES-D) which measures current symptoms of depression.
- 8. Mini International Neuropsychiatric Interview (MINI) suicide subscale to evaluate suicide risk.
- 9. Beck Depression Inventory 2nd Edition (BDI-II) is a severity measure assessing symptoms of depression.
- 10. Generalized Anxiety Disorder-7 (GAD-7): measures severity of anxiety.

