Any changes or amendments to the protocol made in response to adverse events/SAEs will be discussed with [name] and [name], and then requested in writing to the IRB, which will then grant or deny permission to make the requested change in protocol. The DSMB and FDA will be notified about any significant changes to the protocol. NIDA will be informed of any approved changes in protocol by documentation in the noncompetitive continuation application. Changes that significantly alter the scope of the research or the ability of the research to achieve its specific aims will be submitted to [name] and [name], the DSMB, FDA, and NIDA for approval prior to implementation.

26. Withdrawal or Monitoring of Participants

For the participant's protection, participants will be withdrawn immediately from the study if any of the following occur:

- Cardiovascular disease (CVD) event: Typically includes MI (heart attack), PTCA (angioplasty/stenting), bypass surgery, stroke, peripheral vascular disease (arterial blockages in arms or legs leading to procedure or surgery). Less common CVD problems would be new cardiac arrhythmias (e.g., new atrial fibrillation) or new valvular disease (e.g., mitral or aortic regurgitation).
- 2. DVT/PE (deep vein thrombosis/pulmonary embolism, i.e., blood clots in the venous system).
- 3. Suicide Attempt: A participant will be withdrawn if he/she attempts suicide at any time during participation in the study.
- 4. Psychiatric Hospitalization: A participant will be withdrawn if he/she is hospitalized for psychiatric reasons at any time during participation in the study.
- 5. Pregnancy: If participant indicates she is pregnant or has a positive pregnancy test at the Randomization Visit, she will be withdrawn from the study, and this event will remain open until delivery. At that time the licensed medical monitor will contact the participant to ask a

few questions about the baby's health and will update the open 'Adverse Event Form'. A positive pregnancy test at follow-up will trigger an 'Adverse Event Form' to be completed but will not result in withdrawal since she is no longer receiving study product.

6. Expired breath carbon monoxide increase: A participant will be withdrawn from the study if their CO reading is 100 ppm or greater.

The following will be monitored and can lead to the participant being withdrawn by the Pl or Licensed Medical Monitor:

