- Blood pressure (BP) or heart rate (HR) changes: If any of the following occur post-enrollment:
 BP is at or above 160 SBP or 100 DBP, 2) BP is below 90 SBP or 50 DBP 3) HR is at or above 105 bpm, 4) or below 45 bpm.
- 2. Changes in tobacco product use: if during the weekly visits, participants self-report a greater than 100% increase in cigarette per day (total cigarettes, including study and non-study cigarettes) relative to baseline, or a 50% increase in cigarettes per day relative to baseline that is accompanied by an average daily use of 2 ml e-liquid or more."
- 3. Expired breath Carbon Monoxide increase: An 'Adverse Event Form' will be documented and the participant will be monitored by the medical monitor if CO exceeding the following criteria based on Baseline CO:
 - a. CO is greater than 50 ppm if CO at Baseline is < 20 ppm.
 - b. CO is greater than 60 ppm if CO at Baseline is 20 34 ppm.
 - c. CO is greater than 70 ppm if CO at Baseline is 35 49 ppm.
 - d. CO is greater than 80 ppm if CO at Baseline is 50 64 ppm.
 - e. CO is greater than 90 ppm if CO at Baseline is 65 80 ppm.
- 4. Medication changes: If a participant begins taking any of the exclusionary medications or other medications that could potentially have a smoking-drug interaction post- enrollment, the licensed medical monitor will determine how best to monitor and minimize potential risks (including withdrawal if warranted). We will also recommend that a letter be sent to the participant's physician (with their consent), making them aware of the potential changes in smoking that could occur as a result of participation in the study.
- 5. Any hospitalization or debilitation in which participation in the study could be detrimental to the recovery process. This will be self-reported by the participant and will be reviewed by the site PI and medical monitor to determine whether continued participation in the study is appropriate.
- 6. If a participant is behaving in an inappropriate or threatening manner, admits to lying about eligibility criteria, including omitting previous medical diagnoses and medications, is participating in other smoking research studies that could affect the primary outcome measures, does not follow study instructions, etc., then the PI can withdraw him/her from the study at the PI's discretion.

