- 7. If a participant fails to attend his/her Randomization Visit within the 21-day allowable visit window, he/she will not be eligible to reschedule this visit or continue participation in the study.
- 8. If there is reason to believe the participant is sharing the study product with other people.

If a participant chooses to withdraw from the study at any time, we will them to return to the lab to return study product and equipment and to receive their final study payment. We will also ask participants who have been randomized if they would like to complete the end of study questionnaires.

27. Investigational Tobacco Product

The Co-Directors of this Center grant, Drs. [name] and [name], have submitted an Investigational Tobacco Product (ITP) application to the FDA to cover the experimental cigarettes being used in this study.

28. Study Endpoints / Outcomes

28.1. Primary Endpoints:

• Total number of cigarettes smoked per day (i.e. study plus non-study cigarettes) as measured by daily Interactive Voice Response (IVR) phone calls. The total number of cigarettes smoked per day will be averaged using the last 7 days prior to the Week 12 visit. We note that subjects have the opportunity to correct data entry errors in MR from calls made since the last visit at each visit (for example, if a subject entered 100 cigarettes instead of 10 cigarettes). In these cases, the original IVR data will be replaced with the corrected data to create a final, cleaned version that will be used for analysis (herein called "IVR-Revised"). A secondary, repeated measures analysis will also be completed using the mean of the total number of cigarettes smoked per day at each visit, calculated using IVR calls from the previous 7 days. In the event that two visits were less than 7 days apart, then the average will be calculated using only days since the last visit.

28.2. Secondary Outcomes:

- Cigarette smoke exposure: mercapturic acid CEMA
- Smoke-free days: the number of days not smoking any combustible products based on IVR-Revised

28.3. Exploratory Outcomes:

- Cigarette characteristics: CES subscale score for Satisfaction
- Discomfort/dysfunction: MNWS total
- Vaping device use: number of days using assigned vaping device (IVR)
- Study cigarettes per day (CPD): the mean cigarettes smoked per day based on 7 days' Daily Interactive Voice Response (IVR)-Revised data before the week 12 visit.
- Cigarette dependence: Total scores on the FTND

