This is a 2x2x2 factorial design in which participants will be randomized with equal probability to one of eight groups. Randomization will be stratified by age (18-24 vs. 25+) and menthol preference; a set number/percentage of either age and menthol vs. non-menthol preferring smokers will not be enforced. All analyses described below will follow the intent-to-treat principle (i.e. subjects will be analyzed according to their randomized treatment assignment regardless of their compliance) unless otherwise noted.

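### The primary imputation for Week 12 cigarettes per day names only baseline covariates: on-study CPD goes unused, the randomized factors are not mentioned, and a rise in CPD can itself lead to withdrawal

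*Combined protocol and SAP*

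**What the plan says.** **Endpoint and principle.** Section 28.1 makes total CPD from daily interactive voice response (IVR) calls the primary endpoint: "The total number of cigarettes smoked per day will be averaged using the last 7 days prior to the Week 12 visit". Section 29 applies intent-to-treat: "subjects will be analyzed according to their randomized treatment assignment regardless of their compliance".

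**Missing data.** Section 29 gives multiple imputation as the primary approach, with regression models built on baseline covariates. Beforehand, participants with and without missing data are compared to find baseline covariates associated with missingness. Neither the randomized factors nor post-baseline CPD is named as a predictor. Baseline- and last-observation-carried-forward (BOCF, LOCF) are sensitivity analyses. Section 28.1 adds a secondary repeated-measures analysis of CPD by visit. Section 30 assumes 75% retention, or 360 of 480.

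**Withdrawal.** Section 26 introduces a list with "The following will be monitored and can lead to the participant being withdrawn by the" PI or licensed medical monitor. One entry applies if "participants self-report a greater than 100% increase in cigarette per day (total cigarettes, including study and non-study cigarettes) relative to baseline", or if there is a "50% increase in cigarettes per day relative to baseline that is accompanied by an average daily use of 2 ml e-liquid or more".

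**After withdrawal.** When withdrawal is decided by phone or the subject drops out, Section 8.1 says "we will ask the subject to attend an exit visit to return study product and equipment", complete questionnaires and undergo safety assessments. Section 8.2 lists "IVR Review of Daily Call and follow-up on missing and unusual reports and Timeline Follow-back Questionnaire", if needed, at the termination visit. On use of that material it says "The data collected during the termination visit will be used as appropriate given the days outside of visit window" and other considerations, to be settled in data analysis. Section 10 runs daily calls from screening to the Week 12 visit, and the Section 32 schedule shows un-enrolment from IVR at Week 12. Neither addresses withdrawn participants.

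**The concern.** There are two linked issues, and the first is the larger.

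**Imputation model.** A participant who leaves at Week 8 has weeks of daily CPD on file. These should predict Week 12 CPD better than baseline covariates alone, but the described model does not use them. If the model also lacks the randomized factors, imputed values carry no treatment effect and every contrast is pulled toward zero. Interactions are the most exposed. Section 30 gives the half-size interaction a power of only 0.54, and Section 29 removes two-way interactions that are not significant at 0.05.

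**Withdrawal rule.** Withdrawal can follow a rise in the primary outcome itself. For those participants, missing Week 12 CPD depends on observed post-baseline CPD, which is the information the stated model omits. If calls stop at withdrawal, the endpoint window cannot be recovered later.

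**Working it through.** **1. Reproduce the plan's power for CPD (Section 30: difference 6.3, SD 7.2, alpha 0.05, taken as two-sided).** Completers: 480 × 0.75 = 360, so 180 per factor level and 90 per 2×2 cell.
- Half-size main effect: SE = 7.2 × √(2/180) = 0.759; power = Φ(3.15/0.759 − 1.96) = 0.986 (stated 0.99).
- Half-size interaction: SE = 7.2 × √(4/90) = 1.518; power = Φ(3.15/1.518 − 1.96) = 0.546 (stated 0.54).
- The other four CPD cells also reproduce.

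**2. Randomized factors left out of the imputation.** Assume the same missing share m in every group, unrelated to outcome. Observed participants show the full effect and imputed ones show none, so estimated effect = (1 − m) × true effect.

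| m | Source of m | 6.3 becomes | 3.15 becomes |
|---|---|---|---|
| 4% | completely missing weeks in the earlier trial, Section 29 | 6.05 | 3.02 |
| 10% | illustrative | 5.67 | 2.84 |
| 25% | planned non-retention, Section 30 | 4.73 | 2.36 |

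The interaction was simulated at 25% missing (N = 480, true value 3.15, SD 7.2, 2,000 runs, 20 imputations):
- all factors and the interaction in the imputation model: estimate 3.19, power 0.55;
- main effects only: 2.39, power 0.33;
- no randomized factor: 2.40, power 0.28.

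Naming the factors without their interactions is therefore not enough. Power for the 6.3 main effect was 1.00 with the factors omitted. None of these runs includes withdrawal for a CPD rise.

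**3. Withdrawal for a CPD rise, randomized factors in the model.** No rate is given, so assume 2–5% of one cigarette arm is withdrawn after CPD doubles from 12–20. Bias = fraction × (true − imputed Week 12 CPD), imputing baseline in the normal-nicotine (NNC) arm and baseline − 6.3 in the very-low-nicotine (VLNC) arm.
- CPD returns to baseline: 0 to 0.05 × 6.3 = 0.32, or 0–5% of 6.3.
- CPD falls halfway back: 0.02 × (18 − 12) = 0.12 to 0.05 × (30 − 13.7) = 0.82, or 2–13%.
- CPD stays doubled: 0.02 × (24 − 12) = 0.24 to 0.05 × (40 − 13.7) = 1.32, or 4–21%. The top value needs 5% of VLNC, none of NNC, and everyone starting at 20 CPD.

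The cigarette effect is overstated if these withdrawals fall in VLNC and understated if they fall in NNC.

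**4. A separate simulation (300 runs).** Assumed: baseline mean 15 and SD 7 truncated to 5–50, residual SD 7.2, correlation 0.6 between mid-trial and Week 12 residuals, drift +2, and mid-trial VLNC effect 70% of its Week 12 value. Every participant whose CPD rose more than 100% was withdrawn (8.6% NNC, 3.2% VLNC), with 20% other random drop-out. CPD was truncated at zero, so the full-data effect is below 6.3 in size.

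| Method | Estimated effect |
|---|---|
| Full data | −5.82 |
| Imputation, baseline only | −4.13 |
| Baseline + arm | −5.49 |
| Baseline + arm + post-baseline CPD | −5.83 |
| LOCF | −5.59 |
| BOCF | −4.19 |

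With arm included, the remaining bias is (5.82 − 5.49)/5.82 = 6%, here toward the null. With the 20% random drop-out alone, baseline-only imputation already gave −4.65, so most of its shortfall does not come from the withdrawal rule.

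**The case against.** The strongest reply is that the large figures rest on one reading of Section 29. Building models on baseline covariates does not expressly exclude the randomized factors, which are the core terms of the analysis model. A statistician may well include them as routine. This stands: a reader might infer that the plan omits arm and that a 25% loss of effect is established, but the text is silent. Nor is 25% the only missing share to consider. Section 29 expects missing data to be minimal and cites 4% of weeks completely missing earlier, although that figure may not capture drop-out.

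On withdrawal, the rule is discretionary and no frequency is given. Section 1.2 reports that CPD tends to fall on VLNC cigarettes. Section 6.1 dispenses twice the interval's supply; if that is set at baseline CPD, a rise above 100% would need extra pick-ups or non-study cigarettes. The 50% limb does not have that constraint. A reader might infer that the rule inflates the VLNC effect. The documents do not support a direction: the 6% bias in step 4 runs the other way, and equal rates in both arms give an overstatement (2–5%) only if withdrawn participants follow the same CPD course in each arm.

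A reader might also infer that calls stop at withdrawal. No section says so, and none says they continue.

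The prespecified safeguards count for something. LOCF carries the rise forward, and a likelihood-based repeated-measures analysis would use observed CPD. They probe the primary estimate but do not replace it. BOCF helps least: in step 4 it nearly matched baseline-only imputation, so agreement between those two would not reassure.

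**Conclusion.** The point holds as a gap in the primary missing-data method. As described, the imputation leaves unused the CPD already collected from participants without Week 12 data, and that does not depend on how the silence about arm is read. If the randomized factors are also omitted, the 6.3 CPD effect shrinks by about 0.25 at 4% missing, 0.6 at 10% and 1.6 at 25%. At 25% the half-size interaction has about half its planned power. These sizes assume equal missingness across groups, unrelated to outcome. The conclusion on the 6.3 main effect is not at risk for power; its estimated size and the interaction findings are.

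The withdrawal rule is secondary. It makes some missingness depend on observed post-baseline CPD, and the fate of the calls is unstated. Because withdrawal rates and later smoking are assumed throughout, this is a risk of bias of unknown frequency and direction, not a demonstrated bias.

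**What to change.** **Section 29.** State that the imputation model includes the three randomized factors, their two-way interactions, baseline covariates and observed post-baseline CPD, including CPD up to the termination visit. Keep BOCF and LOCF as sensitivity analyses. This costs a few sentences and should be settled before unblinding.

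**Sections 8.1, 8.2 and 10.** Distinguish stopping study product from leaving follow-up. State that automated IVR calls continue to Week 12, or at minimum for the final 7 days, for randomized participants who stop product without withdrawing consent, and that these data enter the intent-to-treat analysis. Report drop-out by arm and reason. No withdrawal trigger needs to change.

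**Cost.** At Section 15 rates, calls from randomization to Week 12 cost at most 84 × $1 + 8 × $5 = $124 per person, within the amount already planned for each participant; the final seven cost $7. For an assumed 5–12 people (2–5% of 240) that is $620–$1,488. If all 120 planned non-completers could be called, the ceiling is 120 × $124 = $14,880. Consent wording, phones kept longer and staff follow-up add to this.

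**Downsides.** Calls after withdrawal would lack the correction made at visits. Some would reflect usual-brand smoking, which can dilute the effect but fits the stated principle. Where calls are not obtained, imputing from an elevated CPD that later fell can over-correct, by up to 7% of 6.3 in simulation, and can then do worse than the current plan. With calls continued as well, simulated bias was at most 2% in every case, so the two changes belong together.
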